9.3.4 Replacement Policy

9.3.4.1 Subjects

In general, subjects who prematurely discontinue from the trial for any reason will not be replaced. An exception may be made for subjects who are unevaluable due to the impact of the coronavirus disease 2019 (COVID-19) pandemic and associated restrictions on movement and work. Subjects unable to receive treatment or be evaluated due to restrictions during the COVID-19 pandemic may be replaced, at the discretion of the Sponsor. This may result in more subjects than originally planned being enrolled into the trial to allow for the originally planned number to be evaluable for the primary efficacy analysis.

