9.6.5.1 Primary and Secondary Endpoint Analysis

The estimand for the primary analysis will use the Treatment Policy Strategy for most intercurrent events; selected intercurrent events leading to data that are missing completely at random may be addressed with a While-on-Treatment Strategy (e.g., if site closures due to COVID-19).

The primary efficacy endpoint is the proportion of responders during Month 6. The proportion of time each subject's sUA is <6 mg/dL will be calculated using observed data at Weeks 20, 21, 22, 23 and 24. The amount of time that sUA is <6 mg/dL (using linear interpolation, if necessary) will be calculated and divided by the total amount of time from the first to the last observed sUA value in this time range (missed values in this time range will be ignored for purposes of this calculation). Subjects who have no available sUA value in this time range will be imputed as non-responders unless the data are missing completely at random, in which case they will be omitted from the analysis. Two-sided exact 95% confidence intervals (CIs) will be calculated.

The primary analysis will be performed on all enrolled subjects who receive ≥ 1 dose of pegloticase with MTX (i.e., the ITT analysis set).

The proportion of Month 3 responders will be summarized similarly to the Month 6 responders. All sUA results collected between infusions from Week 10 through Week 14 of the trial will be used in the calculation of the Month 3 responders.

The mean change from Baseline in in urate deposition volume (measured by DECT) to Week 24 will be summarized along with the corresponding 95% CI for subjects with DECT assessments.

The proportion of subjects experiencing any of the following events: IR leading to discontinuation of treatment, anaphylaxis or meeting Individual Subject sUA Discontinuation Criteria will be presented. For this composite endpoint, each individual component of the composite will be analyzed overall with a summary of the incidence and the corresponding 95% CI.

The primary and secondary endpoints will be summarized overall and by cohort. If Cohort 2 enrolls both subjects with previous mild IR and those with no previous IR, then the data will be summarized by IR category (no IR, mild IR) within Cohort 2 and for Cohorts 1 and 2 combined. No adjustments to CIs will be made for multiple endpoints or multiple time points.

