10. EFFICACY ANALYSES

The ITT analysis set will be used to assess efficacy endpoints. The estimand for the primary analysis will use the Treatment Policy Strategy (data will be used regardless of whether an intercurrent event occurred) for most intercurrent events; the intercurrent event of treatment or study discontinuation related to COVID-19 (leading to data that are missing completely at random) will be addressed with a While-on Treatment Strategy (only values prior to occurrence of intercurrent event will be used).

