11.2 Primary Efficacy Endpoint and Analysis

The primary efficacy endpoint is the proportion of Month 6 (Weeks 20, 21, 22, 23 and 24) responders, defined as subjects achieving and maintaining sUA < 6 mg/dL for at least 80% of the time during Month 6.

The sUA concentrations vs. time (collected to the nearest minute in the CRF) curve will be used to estimate the proportion of time that the sUA is < 6 mg/dL using the available pre-infusion, non-infusion, and post-infusion samples with non-missing sUA values. Central laboratory results from visits at which an infusion was not performed (e.g., subject discontinued pegloticase but remained in study or unscheduled visits) will be used when available.

CCI

CCI

[REDACTED]

[REDACTED]

[REDACTED]

[REDACTED]

[REDACTED]

[REDACTED]

[REDACTED]

CCI

If the subject's proportion of hours, P, is greater than or equal to 80% the subject will be called a responder for the primary efficacy endpoint. A subject with the proportion of hours, P, less than 80% will be counted as a non-responder. Any subject who meets the individual subject sUA discontinuation criteria or discontinues pegloticase with reason of 'Lack of Efficacy', prior to Week 24 will be counted as a non-responder.

For subjects who postponed or missed visits due to COVID-19, only visits occurring prior to any disruption of treatment (> 21 days between infusions) or cessation in treatment will be used for the primary analysis. Any results following the disruption in treatment will be set to missing. Subjects with disrupted treatment due to COVID-19 at any point prior to the Month 6 period will not be included in the primary analysis.

The proportion of hours during the period during which the sUA was less than 6 mg/dL will be summarized using descriptive statistics. If a subject has ≤ 1 data point in the period, then the proportion of hours will not be calculated. The number and proportion of subjects that discontinued treatment due to the stopping rule will be summarized. The number and proportion of responders will be summarized along with a 95% exact (Clopper-Pearson) confidence interval (CI) for the proportion. In addition, the number and proportion of subjects missing all data in the analysis period, subjects with only one measurement above the cutoff in the analysis period, and subjects with only one measurement below the cutoff in the analysis period will be summarized.

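### SAP 11.2 removes subjects with a COVID-19 infusion gap over 21 days from the primary analysis even when their Month 6 sUA was measured, which the protocol does not provide for and SAP 15 does not declare

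*SAP*

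**What the plan says.** **Protocol 9.6.5.1** runs the primary analysis on the ITT set, with a treatment-policy estimand for most intercurrent events. Its exception is limited: "selected intercurrent events leading to data that are missing completely at random may be addressed with a While-on-Treatment Strategy", with COVID-19 site closures as the example. Its omission rule is also limited: "Subjects who have no available sUA value in this time range will be imputed as non-responders unless the data are missing completely at random"; only in that last case is the subject left out.

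**Protocol 9.3.4.1** says that subjects "unable to receive treatment or be evaluated due to restrictions during the COVID-19 pandemic may be replaced, at the discretion of the Sponsor".

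**SAP 10** repeats the "Treatment Policy Strategy (data will be used regardless of whether an intercurrent event occurred) for most intercurrent events". It applies while-on-treatment handling to "the intercurrent event of treatment or study discontinuation related to COVID-19 (leading to data that are missing completely at random"), meaning that only values before the event are used.

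**SAP 11.2** says that for subjects who postponed or missed visits because of COVID-19, "only visits occurring prior to any disruption of treatment (> 21 days between infusions) or cessation in treatment will be used". It continues "Any results following the disruption in treatment will be set to missing", and then "Subjects with disrupted treatment due to COVID-19 at any point prior to the Month 6 period will not be included in the primary analysis". The paragraph before counts as a non-responder anyone who meets the sUA discontinuation criteria, or stops pegloticase for lack of efficacy, before Week 24.

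**SAP 15** states that nothing in the protocol-specified analyses has changed.

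**The concern.** Both protocol conditions concern data that are absent. SAP 11.2 concerns data that may well be present: it sets measured values to missing and then drops the subject because they are missing. It also adds a trigger, a temporary gap with dosing resumed, that is not discontinuation and so lies outside SAP 10. The 21-day figure does not appear in the protocol.

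Three things are at stake.

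- **Denominator.** It comes to depend on whether a gap is attributed to COVID-19, in an open-label trial. A gap of the same length from any other cause leaves the subject in.
- **Bias.** If a gap in exposure lowers the chance of response, the removed subjects are more often non-responders, and the rate and its lower bound are too high. If the gap is unrelated to response, the harm is lost subjects and an undeclared change of analysis population.
- **Rule order.** A subject who has a COVID-19 gap, resumes, and then meets the sUA criteria or stops for lack of efficacy is both a non-responder and not included. The SAP does not say which rule wins, and exclusion would take a known failure out of the denominator.

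**Working it through.** **Inputs.** N = 30, benchmark 20%, success at 12 or more responders, lower bound about 23% (Protocol 9.6.9, SAP 5). Two-sided 95% Clopper-Pearson interval (SAP 11.2). Infusions every 14 days, with visits fixed to Day 1 and windows of ±3 days (Protocol 9.1 and Schedule of Assessments). The number of COVID-19 exclusions is not in the documents; I assumed 1 to 4.

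**1. The plan's own figure.** For x responders of n, the lower bound is the 2.5% quantile of Beta(x, n − x + 1). 12/30 gives 22.66%, which is the plan's 23%. 11/30 gives 19.93%, below 20%. The threshold of 12 is correct.

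**2. How easily the trigger is met.** With no infusion missed and both visits in window, consecutive infusions are at most 14 + 6 = 20 days apart. With one missed, the gap is 28 ± 6, or 22 to 34 days. One missed infusion therefore always exceeds 21 days when the neighbouring infusions are in window.

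**3. Effect on the conclusion.**

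| Observed in 30 | Lower bound | Excluded | Analysed | Lower bound |
|---|---|---|---|---|
| 11 | 19.93% (miss) | 1 non-responder | 11/29 | 20.69% (success) |
| 10 | 17.29% (miss) | 4 non-responders | 10/26 | 20.23% (success) |
| 12 | 22.66% (success) | 2 responders | 10/28 | 18.64% (miss) |

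The fewest responders needed for a lower bound above 20% is 12 at n = 30, 11 at n = 27 to 29, and 10 at n = 26.

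**4. How often one exclusion matters.** P(exactly 11 of 30) is 1.61% at a true rate of 20% and 13.96% at an assumed 40%. If the excluded subject is a random one of the 30, that subject is a non-responder with probability 19/30, so this upward flip has probability 1.61% × 19/30 = 1.02% and 13.96% × 19/30 = 8.84%.

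**5. False success at a true rate of 20%.** This is the binomial probability of reaching the threshold.

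| Excluded | Unrelated to outcome (Binomial with n = 30 − excluded) | Worst case: all non-responders, none replaced (Binomial with n = 30) |
|---|---|---|
| 0 | 0.95% | 0.95% |
| 1 | 1.97% | P(X ≥ 11) = 2.56% |
| 2 | 1.49% | 2.56% |
| 3 | 1.10% | 2.56% |
| 4 | 2.32% | P(X ≥ 10) = 6.11% |

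If every excluded non-responder is replaced by a new subject, the worst case is P(X + Binomial(m, 0.2) ≥ 12), with X from the 30 subjects first enrolled: 1.27% for m = 1 and 2.74% for m = 4.

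**The case against.** The best counter-reading starts from the protocol's own example. A site closure can interrupt treatment without ending it. Under while-on-treatment handling, values after the event are unused by definition, so a subject with a gap before Month 6 has no usable Month 6 value and may be omitted. Protocol 9.3.4.1 also foresees subjects who are not evaluable for the primary analysis because of the pandemic, including some who merely could not be treated. The rule is pre-specified and numeric, COVID-19 deviations are listed under SAP 9.2, and the outcome is a laboratory value.

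Part of this stands. For subjects who have no Month 6 sUA for a COVID-19 reason and meet the missing-completely-at-random condition, SAP 11.2 agrees with the protocol. The direction of bias is not known in advance, and the effect is modest unless several excluded subjects are non-responders. SAP 11.3 also summarises time below 6 mg/dL from all available sUA values, so the excluded subjects' data need not vanish from the report.

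It does not rescue the rule for subjects with measured data. The protocol ties the strategy to events that lead to missing data, and here the data exist until the SAP deletes them. SAP 11.2 itself uses central-laboratory results from subjects who stopped pegloticase but stayed in the study. A subject permanently off drug thus keeps Month 6 values, while one who missed a single infusion for COVID-19 loses them. The replacement clause is an exception for unevaluable subjects; someone who resumed and has complete Week 20 to 24 samples is evaluable. Replacement can restore N but does not bring back the removed outcome.

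Protocol 9.6.5 does say there will be no statistical testing, but Protocol 9.6.9 and SAP 5 still define success by the exact lower bound, so the denominator matters.

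**Conclusion.** The concern holds and should be fixed. For subjects with a COVID-19 gap and measured Month 6 sUA, SAP 11.2 goes beyond both Protocol 9.6.5.1 and SAP 10, and SAP 15 does not say so. The order of the non-responder and exclusion rules is also undefined.

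The departure itself is plain from the text. Its numerical size rests on an assumed 1 to 4 exclusions. One exclusion can reverse a result of 11/30, and two can reverse 12/30 in the other direction. Error above 2.5% requires that the excluded subjects be non-responders, and it is material only at four such exclusions: 6.11% without replacement and 2.74% with it. If exclusion is unrelated to outcome, the error rate stays below 2.5%.

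**What to change.** 1. In the primary analysis, keep every ITT subject with measured Month 6 sUA, including those who resumed after a COVID-19 gap.
2. Omit only subjects with no Month 6 value for a documented COVID-19 reason judged missing completely at random.
3. State that meeting the sUA discontinuation criteria or stopping for lack of efficacy, before or after a gap, is non-response and overrides any COVID-19 omission.
4. Move the >21-day exclusion to a sensitivity analysis, and add one that counts every omitted subject as a non-responder. Parts of SAP 11.3 and the table list are redacted, so check whether either is already there.
5. List each omitted subject, using the COVID-19 deviation flag in SAP 9.2.
6. Align SAP 10 with 11.2, and record any remaining departure in SAP 15.

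The cost is SAP wording and one or two tables; no new data are needed. The primary rate may be slightly less favourable, and it will include subjects whose treatment was interrupted for reasons unrelated to the drug.

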11.5 Analyses of DECT Scans

The observed values and the change from baseline for urate deposition volume, hand erosion score, foot erosion score, and total bone erosion score at each scheduled time point will be summarized using descriptive statistics. A two-sided 95% Wald CI for the changes from baseline will be presented. **CCI**

11.6 **CCI**

CCI

[figure not shown]
CCI

11.7 Analyses of Health Assessment Questionnaire

Observed values and change from baseline in the HAQ-DI, HAQ-Pain, and HAQ-Health score at each scheduled time point will be summarized using descriptive statistics. A two-sided 95% Wald CI for the changes from baseline will be presented.

11.8 Analyses of CCI

[figure not shown]
CCI

11.9 Analyses of CCI

CCI

11.10 Analyses of CCI

CCI

11.11 Analyses of CCI

CCI

11.12 Analyses of CCI

CCI

11.13 Analyses of CCI

Subjects will be assessed for the presence of CCI. The number of CCI will be recorded for the CCI

[figure not shown]
For subjects with CCI █ at baseline, the mean number of CCI █ and change from baseline will be presented by visit. A two-sided 95% CCI █ for the changes from baseline will be presented.

12. CCI

- [REDACTED]
- [REDACTED]
- [REDACTED]
- [REDACTED]

PPD

[figure not shown]
CCI

CCI

[figure not shown]
12.3 CCI

CCI

13. CCI

- 

- 

- CCI
[REDACTED]
- [REDACTED]
[REDACTED]
- [REDACTED]
- [REDACTED]

14. SAFETY ANALYSES

Safety analyses for the MTX Run-in Period will be based on the MTX Analysis Set. Safety analyses for the Pegloticase + MTX Treatment Period and Optional Pegloticase + MTX Extension Period will be based on the Safety Analysis Set.

14.1 Extent of Exposure

Study drug exposure will be summarized for both MTX and pegloticase using the duration of treatment (in days), number of doses, total dosage received, and average doses received.

For the MTX Run-in Period, the following will be summarized using descriptive statistics:

- Duration of treatment defined as the last dose of MTX prior to the Day 1 visit date – first dose date of MTX + 1
- Total MTX dosage (prescribed dose) taken between the first and last dose dates in the MTX Run-in Period, inclusive (in mg)
- Average MTX dose (in mg) (total dosage for the MTX Run-in Period divided by number of doses taken during the MTX Run-in Period)
- Number of subjects with any dose reduction (reduction in prescribed dose for reason of abnormal labs, AE, or titration down).

For the Pegloticase + MTX Period, the following will be summarized:

- Separately for the Pegloticase + MTX Treatment Period, Optional Pegloticase + MTX Extension Period, and overall
 - Number of pegloticase infusions received
 - Duration in days between first and last pegloticase infusion in the given period, defined as last infusion date – first infusion date + 1

- Number of incomplete infusions received
- Number of interrupted infusions
- At each scheduled Pegloticase infusion visit
 - Number of subjects receiving a complete infusion (i.e., full dose administered)
 - Number of infusions administered without interruption
 - Number of subjects with an interrupted infusion
 - Number of subjects not receiving MTX between previous infusion and current infusion
- MTX
 - Duration of MTX dosing during the Pegloticase + MTX Treatment Period, defined as the last MTX date prior to Week 24 – first MTX dosing date (on or after the date of the Day 1 visit) + 1
 - Total MTX dosage (in mg) received during the Pegloticase + MTX Treatment period
 - Average MTX dose (in mg) (total dosage for the Pegloticase + MTX Treatment Period divided by number of doses taken during the Pegloticase + MTX Treatment Period)
 - Number of subjects with any dose reduction (reduction in prescribed dose for reason of abnormal labs, AE, or titration down) in the Pegloticase + MTX Treatment Period.
 - Duration of MTX dosing during the Optional Pegloticase + MTX Extension Period, defined as the last MTX date – Week 24 MTX dosing date + 1
 - Total MTX dosage (in mg) received during the Optional Pegloticase + MTX Extension period
 - Average MTX dose (in mg) (total dosage for the Optional Pegloticase + MTX Extension Period divided by number of doses taken during the Optional Pegloticase + MTX Extension Period)
 - Number of subjects with any dose reduction (reduction in prescribed dose for reason of abnormal labs, AE, or titration down) in the Optional Pegloticase + MTX Extension Period.

For the overall study, the following will be summarized:

- MTX
 - Duration of MTX dosing, defined as the last MTX date – first MTX dosing date + 1

- Total MTX dosage (in mg) received
- Number of subjects with any dose reduction (reduction in prescribed dose for reason of abnormal labs, AE, or titration down).
- Average MTX dosage (in mg) per dose overall

Methotrexate administration and pegloticase infusion details will be listed. The use of prophylaxis treatments will be provided in listings only.

14.2 Adverse Events

Treatment-emergent AEs (TEAEs) will be summarized separately for the MTX Run-in Period using the MTX Analysis Set and for the Pegloticase + MTX Treatment Period using the Safety Analysis Set. TEAEs during the MTX Run-In Period are defined as events with an onset date on or after the first dose of MTX through the first pegloticase infusion, or through 30 days after the last dose of MTX for subjects who do not receive pegloticase. TEAEs during the Pegloticase + MTX Treatment Period are defined as events that occur after the start of the first pegloticase infusion through 30 days after the last dose of pegloticase and MTX (whichever is later).

Partial dates will be imputed. For details on imputation rules, refer to [Appendix A: Presentation of Data and Programming Specifications](#). Imputed dates are only used for classification of TEAEs. If it cannot be determined whether the AE is treatment emergent due to a partial onset date, then it will be counted as such.

Events with missing relationship to study drug in the MTX Run-in period will be considered related to MTX. Events with missing relationship to study drug in the Pegloticase + MTX periods will be considered “related” to MTX and “related” to pegloticase. Missing severities will be considered severe.

Verbatim terms in the eCRFs will be mapped to PTs and SOCs using the MedDRA version 23.1. Adverse event severity will be graded according to Rheumatology Common Toxicity Criteria (CTC) v2.0 [\[Woodworth et al, 2007\]](#).

An overall summary of TEAEs will be provided for the MTX Run-in Period and Pegloticase + MTX Treatment Period, including the number and percentage of subjects with each AE type as well as the number of events for each of the following:

- TEAEs
- Serious TEAEs
- TEAEs Related to MTX
- TEAEs Related to pegloticase (applicable to Pegloticase + MTX Treatment period only)
- Serious TEAEs Related to MTX

- Serious TEAEs Related to pegloticase (applicable to Pegloticase + MTX Treatment period only)
- TEAEs with a Rheumatology CTC grade of 3 or higher
- TEAEs leading to permanent withdrawal of MTX
- TEAEs leading to permanent withdrawal of pegloticase (applicable to Pegloticase + MTX Treatment period only)
- TEAEs Related to MTX leading to permanent withdrawal of MTX
- TEAEs Related to pegloticase leading to permanent withdrawal of pegloticase (applicable to Pegloticase + MTX Treatment period only)
- TEAEs leading to death

An overall summary of post-treatment AEs, AEs that occur more than 30 days after the last dose of pegloticase and/or MTX, will include the number and percentage of subjects with each AE type as well as the number of events for each of the following:

- TEAEs
- Serious TEAEs
- TEAEs with a Rheumatology CTC grade of 3 or higher
- TEAEs leading to death.

The following summaries will be presented:

- Subject incidence of TEAEs and total number of unique TEAEs along with the event incidence rate by MedDRA SOC and PT, for the MTX Run-in Period, Pegloticase + MTX Treatment Period, and post-treatment period.
- Subject incidence of TEAEs by MedDRA SOC, PT, and maximum Rheumatology CTC grade, for the MTX Run-in Period and Pegloticase + MTX Treatment Period. At each level of subject summarization, a subject is classified according to the maximum grade if the subject reported 1 or more events.
- Subject incidence of TEAEs by MedDRA SOC, PT, and closest relationship to MTX (Related/Not Related), for the MTX Run-in Period and Pegloticase + MTX Treatment Period. At each level of subject summarization, a subject is classified according to the closest relationship if the subject reported 1 or more events. Adverse events with a missing relationship will be considered related for this summary.
- Subject incidence of TEAEs by MedDRA SOC, PT, and closest relationship to pegloticase (Related/Not Related), for the Pegloticase + MTX Treatment Period. At each level of subject summarization, a subject is classified according to the closest relationship if the subject reported 1 or more events. Adverse events with a missing relationship will be considered related for this summary.

- Subject incidence of serious TEAEs and total number of unique serious TEAEs by MedDRA SOC and PT, for the MTX Run-in Period and Pegloticase + MTX Treatment Period.
- Subject incidence of TEAEs leading to MTX discontinuation and total number of unique TEAEs leading to MTX discontinuation by MedDRA SOC and PT, for the MTX Run-in Period and Pegloticase + MTX Treatment Period
- Subject incidence of TEAEs leading to pegloticase discontinuation and total number of unique TEAEs leading to pegloticase discontinuation by MedDRA SOC and PT, for the Pegloticase + MTX Treatment Period

Each AE summary will be displayed by cohort and overall. Summaries that are displayed by SOC and preferred terms (PT) will be ordered alphabetically by SOC and by PT within SOC. Event incidence rates adjusted by patient year exposure to study drug will be calculated as the (number of events divided by the total patient-years of exposure to the study drug)*100. The patient-years of exposure for the MTX Run-in Period for each subject who continues into the Pegloticase + MTX Treatment Period will be derived as (first dose date of pegloticase in the Pegloticase + MTX Treatment Period – first dose date of MTX)/365.25. The patient-years of exposure for the MTX Run-in Period for each subject who does not continue in the Pegloticase + MTX Treatment Period will be derived as (last dose date of MTX in the MTX Run-in Period – first dose date of MTX + 1)/365.25. The patient-years of exposure for the Pegloticase + MTX Treatment Period for each subject will be derived as (last dose date of MTX or pegloticase (whichever is later)– first dose date of pegloticase + 1)/365.25.

All AEs will be listed. SAEs, AEs leading to death, AEs leading to permanent withdrawal of MTX, and AEs leading to permanent withdrawal of pegloticase will also be listed.

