The signs and symptoms of severe IRs are usually prolonged (e.g., not rapidly responsive to symptomatic medication and/or brief interruption of infusion) or recurrent following initial improvement. Possible associated signs and symptoms of IRs may include, but not be limited to:

- Respiratory: difficulty breathing with wheezing or stridor; respiratory distress manifested as at least 2 or more of the following: tachypnoea, increased use of accessory respiratory muscles, cyanosis, recession or grunting;
- Upper airway swelling (lip, tongue, throat, uvula or larynx);
- Cardiovascular: hypertension, tachycardia, measured hypotension, a decreased level of consciousness or loss of consciousness;
- Dermatological or mucosal: generalized urticaria (hives), generalized erythema, angioedema or generalized pruritus with skin rash

The Safety Review Team must confirm that the tolerability criteria are not met in Cohort 1, prior to Screening subjects with history of pegloticase-related mild IR for Cohort 2. The Safety Review Team could stop the trial for other significant safety concerns.

If an anaphylaxis event occurs in any subject, further dosing with pegloticase for that subject will be discontinued. Anaphylaxis events will be adjudicated using the Sampson criteria (see [Appendix Error! Reference source not found.](#) for guidance on anaphylaxis and IR symptoms and assessment).

Infusion Reaction

An IR will be defined as any infusion-related AE or cluster of temporally-related AEs, not attributable to another cause, which occur during the pegloticase infusion and for up to 2 hours post infusion. Other AEs that occur outside of the 2-hour window following the infusion may also be categorized as an IR at the Principal Investigator's discretion. Signs and symptoms of the IR and treatments administered will be documented in the medical record and in the eCRF and will be adjudicated.

Examples of AEs not considered possible IRs include, but are not limited to: laboratory abnormalities that are unlikely to have occurred during or within 1 hour following the infusion (e.g., anemia), gout flares, most infectious diseases or the recurrence or worsening of a known chronic medical problem identified in the subject's medical history.

In the event of any potential or suspected IR, the procedures in [Section 9.4.9.2](#) will be performed.

Anaphylaxis

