14.3 Adverse Events of Special Interest

Adverse events of special interest will include infusion reactions (IRs), anaphylaxis, gout flares, and MACE including non-fatal myocardial infarction, non-fatal stroke, cardiovascular death, and congestive heart failure.

IRs and Anaphylaxis

IRs and anaphylaxis reactions are identified by the investigator on the eCRF. The signs and symptoms associated with each event are entered on the eCRF and will be coded to the MedDRA dictionary. IRs and anaphylaxis events, and the associated signs and symptoms, will be summarized in the pegloticase + MTX period by SOC, PT, severity, and the time relative to the most recent pegloticase infusion. Time relative to the most recent pegloticase infusion will be categorized as: during infusion, \leq 2 hours after infusion, $>$ 2 hours to 24 hours after infusion, $>$ 24 hours after infusion, and missing (time of event is missing).

If 3 or more events of anaphylaxis occur, events will also be reviewed by an external adjudication committee. Events as reviewed by the external adjudication committee will be summarized separately.

The following search algorithm will be used to identify possible IR and anaphylaxis cases:

Infusion Reaction

- All IRs reported by investigators based on the protocol definition and reported on the eCRF.
- All other AEs that occur after start of infusion and up to 24 hours following the end of the infusion or on the same day of infusion if the start time is missing.

Anaphylaxis

- Any anaphylaxis reported by investigators based on the NIAID/FAAN criteria and reported on the eCRF.
- Any anaphylactic reactions identified by the algorithmic MedDRA SMQ Anaphylactic reactions.

The number and percentage of subjects with IRs including anaphylaxis (investigator reported) will be summarized overall and by severity of event by the following categories for both **CCI**

[REDACTED]:

- **CCI** [REDACTED]
- [REDACTED]
 - [REDACTED]
 - [REDACTED]
 - [REDACTED]
- [REDACTED]
 - [REDACTED]
 - [REDACTED]

Cardiovascular Events

Cardiovascular events will include Major Adverse Cardiovascular Events (MACE), including non-fatal myocardial infarction, non-fatal stroke, cardiovascular death, and congestive heart failure. The following search algorithm will be used to identify possible MACE:

- For cardiovascular death any fatal case plus:

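### The MTX Run-in and Pegloticase + MTX windows for treatment-emergent AEs overlap during the first infusion, so an event then also enters the general run-in tables and rates

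*SAP*

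**What the plan says.** SAP 14.2 gives two windows for subjects who go on to pegloticase. Run-in events are "events with an onset date on or after the first dose of MTX through the first pegloticase infusion". Pegloticase + MTX events are "events that occur after the start of the first pegloticase infusion through 30 days after the last dose of pegloticase and MTX", whichever of the two drugs was given later. Protocol 9.6.7 closes the run-in window and opens the next one in the same way.

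The general tables are produced per period and include "Subject incidence of TEAEs and total number of unique TEAEs along with the event incidence rate by MedDRA SOC and PT". The rate is the "number of events divided by the total patient-years of exposure to the study drug)*100". For subjects who continue, SAP 14.2 takes run-in exposure as the "first dose date of pegloticase in the Pegloticase + MTX Treatment Period" minus the first MTX date, with no day added. Exposure in the next period starts on the first pegloticase date and does add a day.

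Infusion reactions and anaphylaxis have their own summary in SAP 14.3, which "will be summarized in the pegloticase + MTX period by SOC, PT, severity" and timing relative to the infusion.

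**The concern.** The run-in window closes at the end of the first infusion, but the next window opens at its start. An event between those two points satisfies both definitions, and nothing assigns it to one period. Infusion reactions are likely to fall in this interval, because Protocol 9.5.4.1.1 defines them as AEs "which occur during the pegloticase infusion and for up to 2 hours post infusion".

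The run-in tables should describe the weeks on MTX before any pegloticase in this trial. If first-infusion events enter them, the count includes events that began after pegloticase had started, and the rate divides those events by exposure that excludes the infusion day. The run-in exposure is short, so each added event moves the rate visibly.

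**Working it through.** The documents state no AE count or rate, so there is no figure to reproduce. The check applies the definitions to test events and then sizes the effect.

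**1. Which window takes which event.** The run-in definition refers to onset date, but it could also be programmed by clock time to the end of the infusion. Both readings are shown.

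| Event | Run-in, by onset date | Run-in, by clock time | Pegloticase + MTX |
|---|---|---|---|
| Day 1, 1 hour before infusion | in | in | out |
| Day 1, mid-infusion | in | in | **in** |
| Day 1, 1 hour after infusion ends | in | out | **in** |
| Day 2 | out | out | in |

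The mid-infusion event is in both windows on either reading. The post-infusion event is in both only by onset date. If the run-in window closes before the start of the infusion, no test event falls in both.

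**2. What the SAP's other rules do with the infusion day.**
- *Exposure (SAP 14.2).* Run-in person-time stops the day before the first infusion, and person-time in the next period includes that day. The denominators meet without overlap, but the numerators overlap.
- *Partial dates (SAP Appendix A).* An AE whose known month is that of the first infusion, but not that of the first MTX dose, is imputed to the infusion date and assigned to the Pegloticase + MTX Period. Both periods are named when MTX and pegloticase started in the same month (or in the same year, if only the year is known), or when the start date is wholly missing. So an onset imputed to Day 1 gets one period, while an onset known to be during the first infusion gets two.
- *Gout flares (SAP 14.3).* Flares are counted only in the period of onset. The general tables have no such rule.

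**3. Size per event.** Inputs are 30 subjects (SAP 5) and a 6-week run-in, or 42 days (SAP 4). The calculation assumes that all 30 complete the run-in and that nobody else contributes exposure.
- Run-in exposure: 30 × 42 / 365.25 = 3.45 patient-years.
- Added rate per doubled event: 100 / 3.45 = 29.0 per 100 patient-years. Two events add 58.0.
- Added incidence: at most 1/30 = 3.3 percentage points, and only if that subject has no other run-in event.

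The MTX analysis set (SAP 8) also includes run-in failures, whose exposure lowers these figures. For illustration, 10 failures with 21 days each give (1,260 + 210) / 365.25 = 4.02 patient-years, and one event then adds 24.8.

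SAP 14.2 also shows AE summaries by cohort. For Cohort 1 at its target of 10, on the same no-failure assumption, exposure is 10 × 42 / 365.25 = 1.15 patient-years, and one event adds about 87 per 100 patient-years.

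**4. Relative size.** The proportional rise is the number of doubled events divided by the number of genuine run-in events, whatever the exposure. The documents give neither number. If there were 10, 20 or 40 genuine run-in events, one doubled event would raise the rate by 10%, 5% or 2.5%, and two would raise it by 20%, 10% or 5%.

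**The case against.** The best defence is that the SAP shows its intent elsewhere. The exposure formula and the partial-date rule both treat the infusion day as pegloticase time, and where the SAP wants an event in both periods it says so. A careful programmer might therefore read the run-in window as ending when the infusion starts. This is good evidence of intent, but it does not remove the problem. The same paragraph uses the word through inclusively for the 30-day limit, so the literal rule gives the double count, and the intended rule has to be inferred from other sections.

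Other limits on the point stand in full:
- A reader might infer that all of Day 1 overlaps. It does not. Events before the infusion fall outside the Pegloticase + MTX window.
- A reader might infer that the trial's assessment of reactions on re-exposure is distorted. It is not. The infusion reaction and anaphylaxis summary (SAP 14.3) covers the pegloticase period. The composite endpoint (SAP 10.1.2 and 11.4) counts subjects from Day 1. The tolerability criteria (Protocol 9.5.4.1.1.5) count severe reactions and anaphylaxis related to the infusion. None of these uses the run-in window.
- A reader might infer that pegloticase reactions would be attributed to MTX. The run-in tables split events by relationship to MTX, so a reaction judged unrelated to MTX would be shown that way. Only a missing relationship defaults to MTX.
- The two periods are summarized separately, and SAP 14.2 describes no table that pools them. The damage is to the run-in tables, not to a combined total.

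**Conclusion.** The overlap is real on the text of SAP 14.2 and Protocol 9.6.7, and it contradicts the SAP's exposure formula and partial-date rule. Its effect is confined to the general run-in event counts, subject incidence and rates. Overall, one doubled event adds at most about 29 events per 100 patient-years, assuming 30 subjects with 42 days each and no run-in failures. The figure is larger within a cohort. The number of such events is unknown, because the documents give no first-infusion event rate, so the total effect cannot be stated.

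This is a minor correction to a stated rule. It does not support a claim that the run-in rate will certainly be inflated, since there may be no such events, or the rule may be programmed as the other sections suggest. No efficacy endpoint, enrollment decision or infusion reaction result depends on it.

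**What to change.** In SAP 14.2, end the run-in window before the start of the first pegloticase infusion, by date and time, for subjects who receive pegloticase. Make the same change in Protocol 9.6.7. If an amendment is not warranted for this alone, record it in SAP 15, which at present reports no changes to the protocol's analyses.

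Add one rule for ties: a Day 1 event with no onset time goes to the Pegloticase + MTX Period only. This agrees with the exposure formula in SAP 14.2. It also agrees with the search rule in SAP 14.3, which treats an AE on the infusion day with no start time as a possible infusion reaction. The downside is small: a few Day 1 events that began before the infusion, but have no recorded time, may be placed in the later period.

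The cost is a phrase and a sentence, made before database lock. No new data are needed, because SAP 14.3 already relies on AE start times.
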